### **Analysis strategy**

Feasibility and acceptability will be measured through high study retention (70%) and recruitment (recruitment of all participants within 24 months) in our groups. Additional items of acceptability include high scores on treatment satisfaction and credibility/expectancies that are equal or higher to the NicoBloc group. Medication adherence is a third primary outcome with expected differences between our groups. Adherence is notoriously difficult to determine. Self-reported adherence is not always reliable, particularly during treatment studies where there is a demand characteristic to report the desired targeted behavior (e.g., adherence to medication). The behavioral methods described under the assessment section represent the best available self-report tools for determining NRT adherence (e.g., Timeline Follow Back (TLFB) report, returning used products and packaging). Adherence will be defined by self-report using the TLFB and verified through returned patches and packaging. Good adherence is defined by taking greater than 80% of doses of medication at each time point.

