#### **Procedure**

A urine drug screen and pregnancy test for females will be obtained during the screen visit. If positive, participants will be screen failures and will not be enrolled in the study. Specimens will not be

distributed or stored. They will be labeled with a unique study identifier. There will be no clinical data associated with the specimens. They are used only to establish eligibility for the study.

After eligibility determination and consent to participate, the baseline assessments will be administered. This assessment is expected to take about 60 minutes and will provide basic smoking history, smoking behavior, and proposed mediators and moderators such as treatment interest, expectancies for NRT and NicoBloc, previous use of NRT, craving, withdrawal, and side effects associated with NRT use (see Table 1 description) and will be repeated during the study period (see Table 2 for assessment schedule). At each visit the participant will have a carbon monoxide test (CO) which will determine how much CO is in the lungs. At the baseline visit, participants will be asked to prolong smoking as long as they can on the days of the study sessions. Female participants will be screened monthly for pregnancy.

Participants will be randomized to either NicoBloc or Nicotine Lozenge and will undergo the following interventions. Interventionists will be undergraduate level research assistants (RAs) with degrees in psychology or a related field. They will be trained to follow the manual and deliver both behavioral interventions by the PI, although they will not have extensive tobacco training. All sessions will be audiotaped and 20% will be coded for treatment fidelity to ensure no contamination between behavioral interventions.

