A Pilot Trial Comparing NicoBloc to Nicotine Lozenges: Initial Acceptability and Feasibility Trial 2/2/2022 NTC:300001370

Data Analytic Approach

Participant screening, baseline eligibility, baseline attendance, study eligibility, and retention rates throughout the study were calculated overall and per time point. Retention rates between groups at each time point and other dichotomized variables such as adherence were assessed using Chi-Square analyses. Participant demographics and baseline smoking characteristics were assessed, and group differences examined using measures of effect size (Cramer's *V* and Cohen's *d*). Group differences over time were analyzed using generalized estimating equations (GEEs) with all available data (i.e., Intent-To-Treat analyses). GEE results were followed-up with pairwise comparisons when applicable. Measures administered pre- and post-session (QSU and MNWS) were calculated as a change score and included as such in GEE analyses. Pre-session scores were subtracted from post session scores such that negative scores reflect decreases in withdrawal symptoms or smoking urges throughout the session. For measures administered at two or less time points, *t*-tests were used to examine group differences.

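### For scores with a Week 0 value that are compared between groups at a follow-up visit, the SAP's t-tests and single-visit comparisons name no baseline adjustment, which probably costs some precision at about 20 per arm

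*SAP*

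**What the plan says.** The SAP's Data Analytic Approach is a single paragraph. For repeated measures: "Group differences over time were analyzed using generalized estimating equations (GEEs) with all available data", which it equates with intention to treat. It adds that "GEE results were followed-up with pairwise comparisons when applicable". It then turns to less frequent measures: "For measures administered at two or less time points", t-tests compare the groups. No covariate is named in any model, and the text does not say whether Week 0 enters the GEE as a response or how time is coded.

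Baseline data have one stated use: "Participant demographics and baseline smoking characteristics were assessed, and group differences examined using measures of effect size". The only change scores described are within-session (post minus pre) for the QSU and MNWS, which do not adjust for Week 0.

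The protocol (Purpose) places the baseline assessment before randomisation. Under Procedure, that assessment includes "proposed mediators and moderators such as treatment interest, expectancies for NRT and NicoBloc", and it "will be repeated during the study period (see Table 2 for assessment schedule". CO is measured at every visit. Under Analysis strategy, acceptability includes "high scores on treatment satisfaction and credibility/expectancies that are equal or higher to the NicoBloc group", which is a between-group comparison.

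**The concern.** A score taken before randomisation usually predicts the same score later. A t-test on the follow-up score, or a pairwise group comparison at one visit, leaves that information unused. The cost is a wider interval. Seen within the one trial that is run, it also means that a chance difference between arms at Week 0 carries through in part to the reported follow-up difference. With about 20 per arm such differences are common, and the baseline scores are already collected.

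The point covers only scores that have a Week 0 value and are later compared between groups at a follow-up visit. Retention, recruitment, adherence and within-session QSU/MNWS change lie outside it.

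**Working it through.** The documents give no SD, correlation, effect size or power, so there is no planned figure to reproduce.

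**Inputs**
- Total 40 in two arms (protocol, Purpose). 20 per arm assumes 1:1 allocation, because no ratio is stated.
- Retention target 70% (protocol, Analysis strategy): 0.70 × 20 = 14 per arm.
- Assumed: baseline to follow-up correlation r of 0.3, 0.5 and 0.7. k is follow-up SD divided by baseline SD.

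**Adjusted against follow-up-only, one visit**

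Variance ratio = (1 − r²) × (N − 3)/(N − 4). The second factor is the price of estimating one covariate: 37/36 = 1.028 at N = 40 and 25/24 = 1.042 at N = 28. The ratio does not depend on k.

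| r | N = 40 | variance cut | N = 28 | variance cut |
|---|---|---|---|---|
| 0.3 | 0.935 | 6% | 0.948 | 5% |
| 0.5 | 0.771 | 23% | 0.781 | 22% |
| 0.7 | 0.524 | 48% | 0.531 | 47% |

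A simulation of 20,000 trials per setting gave 0.937, 0.781 and 0.521 at N = 40, and 0.949, 0.787 and 0.531 at N = 28.

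Break-even r = √(1 − 1/factor): √(1/37) = 0.164 at N = 40 and √(1/25) = 0.200 at N = 28. At r = 0 the loss is 2.8% and 4.2%.

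**The same loss seen through chance imbalance** (not an additional harm)

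The SD of the baseline mean difference is √(2/20) = 0.316 SD, so the chance of a difference above 0.5 SD is 11% per measure. At 14 per arm it is √(2/14) = 0.378 and 19%, if dropout is unrelated to baseline. With k = 1, a 0.5 SD imbalance shifts a follow-up-only contrast by 0.5r: 0.15, 0.25 and 0.35 SD. An adjusted estimate shifts by about 0.

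**Adjusted against raw change from Week 0, N = 40**

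Variance ratio = k²(1 − r²) × factor / (k² + 1 − 2rk).

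| r | k = 1 | k = 1.5 |
|---|---|---|
| 0.3 | 0.668 | 0.895 |
| 0.5 | 0.771 | 0.991 |
| 0.7 | 0.874 | 1.026 |

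The gain over change therefore runs from 33% to −3%, depending on r and the SD ratio.

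**If the GEE target is a linear slope over time**

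Assume the score is taken at Weeks 0, 1, 2, 3, 4, 8, 12 and 16, with equal correlations.
- With Week 0 the mean time is 46/8 = 5.75, and the time sum of squares is 494 − 8 × 5.75² = 229.5.
- Without Week 0 it is 494 − 46²/7 = 191.7.
- The slope variance therefore rises by 229.5/191.7 = 1.20, about 20%, if Week 0 is removed from the response.
- The weight of Week 0 in the slope, scaled to 16 weeks, is 16 × 5.75/229.5 = 0.40, so the slope is not a raw change from Week 0.
- A Week 0 main effect leaves the group-by-time slope unchanged. In simulation the slope was identical with and without it.

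**The case against.** The strongest reply is that no affected analysis is firmly established. The protocol (Procedure) lists expectancies as proposed mediators and moderators, for both products and before assignment. The credibility/expectancy item under Analysis strategy may be a rating of the assigned treatment on another instrument. The assessment schedule is not in the text available, which is no fault of the plan. CO is not named in the SAP, and the protocol's request about smoking on session days is made at the baseline visit, so Week 0 and later CO may be taken under different conditions. All of this stands, and it is why the point is conditional.

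Three stronger readings are tempting, and the documents support none of them.
- A reader might infer that the comparisons are biased. Randomisation makes both the follow-up-only and the change contrast unbiased on average.
- A reader might infer that Week 0 is ignored everywhere. The SAP does not rule out Week 0 as a GEE response; it simply does not say.
- A reader might infer that any GEE contrast over time is raw change, so that moving Week 0 to a covariate always helps. That equivalence needs categorical visits, and the SAP does not state the time coding. For a linear slope, removing Week 0 loses precision.

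It is also fair that using Week 0 only as a covariate drops anyone with no follow-up score, which sits badly with the SAP's commitment to use whatever data exist when the retention target allows 30% attrition. That is a real cost and shapes the fix.

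Finally, the SAP does report baseline group differences as effect sizes, so imbalance in those characteristics will be visible. Seeing an imbalance does not remove its effect on the comparison.

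**Conclusion.** The point holds for t-tests and single-visit group comparisons of a score that also has a Week 0 value: expectancies if the instrument is the same, and CO only if it is an analysed outcome. Craving and withdrawal come in only if analysed as levels, which the SAP does not describe.

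Against a follow-up-only comparison, adjustment probably yields a useful gain and risks very little. The size rests on 1:1 allocation, complete data at the stated numbers and the assumed r, none of which the documents supply. Against raw change the advantage may be small or absent, and for a linear-time slope there is no claim.

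Priority is low. The trial is a pilot centred on feasibility, acceptability and adherence, no confirmatory test is stated, and the retention, recruitment and adherence results are untouched.

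**What to change.** - **T-tests.** Where a follow-up score is to be compared and a Week 0 score exists, use ANCOVA on the follow-up score with Week 0 as covariate.
- **GEE.** State how time and Week 0 enter. Treat visit as categorical and report visit-specific (or averaged follow-up) group differences adjusted for Week 0, in one of two forms. Either Week 0 is a covariate, or Week 0 stays in the response with its mean constrained equal across arms. The second form keeps participants with no follow-up in the model; the first drops them, and the SAP should say so if it is chosen. The second form adjusts only through the working correlation, so an independence structure would leave the follow-up difference unadjusted; name the structure.
- **Linear slope.** If this is the target, keep Week 0 in the response.
- **Completed analyses.** The SAP is written in the past tense. If results exist, report the adjusted estimates beside the originals and label them as added.
- **No change** to within-session QSU/MNWS change scores.

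The cost is SAP wording and a refit of the affected models. No new data are needed. The covariate form also spends one degree of freedom per model, which is already in the net figures, and carries the loss of participants noted above.

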NicoBloc: NicoBloc participants will be provided with NicoBloc to use in each 30-minute session and will test smoking their conventional cigarette with NicoBloc. In session, they will discuss their experience of smoking their cigarette with NicoBloc at each of the sessions. For Session 1, participants will use one drop of NicoBloc (which will block 33% of tar and nicotine) on their conventional cigarette and then will smoke this cigarette in session. Following smoking, they will discuss the effects of the NicoBloc on their withdrawal, cravings, and overall enjoyment of their cigarette. To bolster their in vivo NicoBloc experience, participants will be provided with NicoBloc to use between sessions to acclimate to the NicoBloc and to make practice quit attempts (PQAs). Sessions 2 and 3 are similar to Session 1 except they will use more NicoBloc product during the session and will be instructed to use the product between sessions. For example, in Session 2, they will use 2 drops on their cigarettes (which blocks about 66% of tar and nicotine) and then smoke. Similarly, in Session 3 they will use 3 drops of NicoBloc which is equivalent to blocking 99% of the tar and nicotine exposure from a cigarette and then smoke. At Session 4 they will discuss their experiences using NicoBloc and will set a quit date prior to their 8 week visit. Participants will return at 8 and 12 weeks (EOT) with a final one month follow-up at Week 16.

Nicotine Lozenge: Participants who receive nicotine lozenge (mini lozenge) will be given either a 2 or 4 mg lozenge to use in session, depending on how soon they smoke after waking. If a participant smokes within 30 minutes of waking, they start with the 4 mg lozenge; more than 30 minutes, they start with the 2 mg lozenge. Similar to NicoBloc, they will use the lozenge in session and will discuss the effects of using the lozenge in session. They will do this for all four Sessions and will be given lozenges between sessions to make PQAs. They will be asked to set a quit date during Session 4 similar to the NicoBloc participants.

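### QSU and MNWS are analysed only as within-session change, so a between-session effect on craving or withdrawal is not credited and can, under certain conditions, count against the arm that achieves it

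*SAP*

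**What the plan says.** The SAP, under Data Analytic Approach, fixes the form of these two outcomes: "Measures administered pre- and post-session (QSU and MNWS) were calculated as a change score and included as such in GEE analyses". The direction is post minus pre: "Pre-session scores were subtracted from post session scores such that negative scores reflect decreases in withdrawal symptoms or smoking urges throughout the session". The model is described as follows: "Group differences over time were analyzed using generalized estimating equations (GEEs) with all available data (i.e., Intent-To-Treat analyses". No baseline or pre-session covariate is named, and no model of pre-session or post-session levels is stated.

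The protocol, under Procedure, has both arms using product away from the sessions. For NicoBloc, "participants will be provided with NicoBloc to use between sessions to acclimate to the NicoBloc and to make practice quit attempts (PQAs". For the lozenge arm, participants "will be given lozenges between sessions to make PQAs". The same section lists "craving, withdrawal, and side effects associated with NRT use" among the things measured at the baseline assessment and repeated later. Under Purpose, that assessment is placed before randomisation.

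**The concern.** Subtracting the pre-session score amounts to adjusting for it with the coefficient fixed at 1. At Session 1 that score precedes any product use. From Session 2 on it follows a period in which both arms have had product, so part of the treatment effect may already be in it.

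An arm difference in pre-session score is plausible, though the documents do not show one. One arm uses nicotine lozenges between sessions; the other uses a fluid described as blocking roughly 33%, 66% and then 99% of tar and nicotine as the drops increase. Session-day smoking is also subject to an instruction: "participants will be asked to prolong smoking as long as they can on the days of the study sessions". Its wording is unclear, and it applies to both arms, but it too bears on the score at arrival.

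If one arm arrives with less craving, it may have less room to fall during the session. Its between-session gain is then either absent from the only stated analysis or enters it with the wrong sign. The pilot's stated purpose includes an early reading of NicoBloc's impact relative to lozenges, and craving and withdrawal are put forward as possible mediators or moderators. A hidden or reversed difference could therefore mislead the design of a later trial.

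**Working it through.** **Inputs from the documents.** The outcome is post minus pre, analysed by GEE without a named covariate (SAP). There are 40 participants (Protocol, Purpose). Product is supplied between sessions in both arms (Protocol, Procedure). Of the lozenge arm's in-session use, the protocol says "They will do this for all four Sessions".

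**Assumptions.** The documents give no SD, pre/post correlation, between-session effect, error rate or power, so there is no figure of the plan's to reproduce. I assume pre/post measurement at Sessions 1–4, because the assessment schedule (Table 2) is not in the text available to me. I also assume 20 per arm. The quantities b, d, τ and r below are assumed and shown as ranges.

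**Step 1: what the change score estimates.** In SD units, let post = a + b·pre − τ·arm + error, with the arm lowering the pre-session score by d. Then the arm differences are:

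- pre-session level: −d
- post-session level: −(b·d + τ)
- change: −(b·d + τ) + d = (1−b)d − τ

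A positive value makes the arm look worse. The sign reverses only if b < 1 and τ < (1−b)d. With b = 1 and τ = 0 the change contrast is 0: the benefit is hidden, not reversed.

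**Step 2: size at one affected session, τ = 0.**

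| d (SD) | b = 0.3 | b = 0.5 | b = 0.7 |
|---|---|---|---|
| 0.25 | 0.175 | 0.125 | 0.075 |
| 0.50 | 0.350 | 0.250 | 0.150 |
| 0.75 | 0.525 | 0.375 | 0.225 |

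The range is 0.075–0.525, or 0.08–0.53 SD after rounding.

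**Step 3: averaged over sessions.** Session 1 is unaffected. With equal weights over four sessions the shift is 3/4 of the tabled value: 0.75 × 0.075 = 0.056 to 0.75 × 0.525 = 0.394 SD.

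**Step 4: simulation check.** An exchangeable GEE was simulated with 20 per arm, four sessions, d = 0.5 at Sessions 2–4 only, and 300 runs.

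- With τ = 0, the mean change difference was +0.25, +0.17 and +0.12 SD for b = 0.3, 0.5 and 0.7. Step 3 predicts 0.75 × 0.35 = 0.26, 0.75 × 0.25 = 0.19 and 0.75 × 0.15 = 0.11.
- The arm was significantly worse in 19%, 19% and 14% of those runs, against 4% with d = 0. These rates also depend on the simulated correlation structure, which the documents cannot settle.
- With b = 0.5 and τ = 0, the post-session level differed by −0.20 SD, so the same arm looked better on level. The formula gives −0.75 × 0.5 × 0.5 = −0.19.
- With b = 0.5 and τ = 0.25 or 0.50, the change difference was −0.07 or −0.30 SD, so the arm looked better on change too. The formula gives 0.19 − 0.25 = −0.06 and 0.19 − 0.50 = −0.31.

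**Step 5: precision at Session 1.** With equal pre and post variances (set to 1) and correlation r, the change score has variance 2(1−r). The post-session score adjusted for the pre-session score has variance 1−r². The ratio is (1−r²)/[2(1−r)] = (1+r)/2, which is 0.65, 0.75 and 0.85 for r = 0.3, 0.5 and 0.7.

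**The case against.** The SAP says plainly that the score describes what happens during the session, and participants use the product in session and discuss its effects there. For that acute question, post minus pre compared between randomised arms is a legitimate contrast. If an arm arrives with less craving and falls less, the smaller fall is real. It misleads only when read as overall control of craving or withdrawal, and the documents do not say it should be read that way. This stands. The fault is that change is the only stated analysis, not that it is invalid.

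A reader might infer that better between-session control will be scored as worse treatment. The documents do not support that. Both arms are active, nothing shows that their pre-session scores differ or in which direction, Session 1 is untouched, and an in-session benefit above (1−b)d restores the expected sign.

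A reader might also infer that baseline craving and withdrawal scores go unused. The text supports only that no baseline covariate is named. It does not say which instruments were used at Week 0, and the SAP does compare baseline smoking characteristics between groups.

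Finally, adding each session's own pre-session score as a covariate might seem the natural remedy. After Session 1 this conditions on a variable that treatment may have altered, and it still gives no credit for what happened between sessions.

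**Conclusion.** The point holds as a minor one. As planned, the QSU and MNWS analysis cannot credit a between-session reduction, and it can make the better arm look worse when b < 1 and the in-session benefit is below (1−b)d. Without an in-session benefit the shift is 0.08–0.53 SD at an affected session and about 0.06–0.39 SD over four sessions. Both ranges rest wholly on the assumed b and d; the four-session range also assumes pre/post measurement at Sessions 1–4. The Session 1 precision gain rests on equal variances and assumed r.

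The consequence is limited. Retention, recruitment, acceptability and adherence carry the pilot's main conclusions (Protocol, Analysis strategy), and none of them depends on this choice. What is at risk is the reading of a secondary signal that a later trial might build on.

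**What to change.** 1. Keep the change score, but state that it measures the acute within-session effect only and not overall craving or withdrawal control.
2. Add, for each scale, a GEE of the pre-session level from Session 2 onward and a GEE of the post-session level. Adjust each for a score taken before any product use: the Week 0 score if the same scale was given then, otherwise the Session 1 pre-session score. Week 0 is preferable because it also precedes randomisation.
3. After Session 1, do not adjust for the same session's pre-session score.
4. For the Session 1 comparison, replace the change score with the post-session score adjusted for the pre-session score.

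The cost is a few sentences in the SAP and a few extra models for non-primary outcomes. The pre- and post-session scores are already collected, so no new data are needed. The SAP is written in the past tense, so if results have already been seen, the added models should be reported as additions to the plan.
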